Imprints Cares is a local early education nonprofit that has been providing services in Forsyth County for the past 50 years. Two services provided by Imprints Cares are important to this project. One, Pediatric Parenting Connections (PPC), forms a partnership with medical providers by embedding a certified parent educator into local health clinics, Westgate Pediatrics, Downtown Health Plaza, and Winston East Pediatrics. This program serves as short term in-office parenting education for breastfeeding, behavior, and developmental concerns. It also serves as a referral point for the more intensive, Parents as Teachers (PAT) home visitation model. Both models are two-generation models devoted to addressing health disparities, promoting maternal health, and mitigating chronic toxic stress. Providing supports that recognize these challenges help young moms obtain positive outcomes^{iv}. Intervening early with a two-generation approach can have positive effects for both young moms and children. There also are societal benefits in that the lifetime benefits of supporting young moms and promoting healthy birth spacing exceed those of the costs^{v, vi, vii, viii}. The benefits of providing parenting support to young moms can include mother's education, use of contraception, healthy birth spacing, child immunization compliance, reduction of child behavior problems (possibly), improvements in the home environment, and parents' realistic expectations for children^{ix, x, xi}. The application of these services to young mothers comprises our Young Moms Program (YMP). As a community we are just beginning to realize the unintended outcome of COVID, one of which appears to be an increase in teen births.

As we continue to recover from the impact of the global pandemic, we must look closely at the significance home visiting programs have on creating authentic relationships with families, which in turn create opportunities for working with young moms to solve problems, achieve personal goals, and access essential resources. According to a Washington State Institute for Public Policy study (2004) Parents as Teachers had the largest benefit per dollar of cost (\$1.23) of all pre-kindergarten early education programs. Imprints Cares traditional PAT program costs \$3,436 per family annually,

Protocol version:

Template updated 9.24.14

which is a return on investment of \$4.70 – 5.60 in future educational remediation, juvenile delinquency, teen pregnancy, substance abuse, and mental illness ^{xv}. Providing support to young moms in Forsyth County is something we cannot afford *not* to do.

Our project will address this emerging health crisis at a time when value-based care models as part of Medicaid transformation are rolling out throughout North Carolina and all programs have had to adapt to changing the delivery mechanisms to more remote offerings. During the pandemic, Imprints Care developed a hybrid model for provision of services through Parents as Teachers. Imprints Cares evidence-based Parents as Teachers hybrid model may have far reaching implications in establishing a pediatric value-based model that can be replicated throughout our community, state, and country. Since January 2021, Wake Forest Baptist Medical Center (WFBMC) has documented 82 births to young moms ages 14 through 21. Since July 2020 Imprints Cares family educators have received approximately 400 referrals from pediatricians with more than 320 families being served, 80%.

Further, as we are considering the intersection of equity with health and social policy, the YMP is an opportunity to directly address disparities in behaviors such as breastfeeding, completion of developmental screenings, and enrollment in early intervention that may be correlated with different demographic groupings. We know that while COVID-19 was traumatic for everyone, young children growing up in poverty were disproportionately impacted. The true impact of the pandemic and public health precautions (i.e., isolation) is just beginning to emerge. We continue to see increased trends in pregnancy in young moms, toxic stress and child maltreatment, food insecurity, and developmental/ behavioral regression in young children. As we enhance opportunities for young moms based on positive outcomes during the pandemic, we can rapidly embed responses to traumatic events into our approach. To the extent that some young moms are perpetuating a multi-generational pattern of early births, the proposed hybrid program is an opportunity to break a cycle linked to poor outcomes for young moms and their children.

Objectives

The objectives of this study are to assess cost-effectiveness of a Young Moms Program that incorporates a traditional Parents as Teachers home visiting parenting program to that of a hybrid virtual/home based Parents as Teachers program, against short-term outcomes, which in turn will serve as leading indicators of longer-term results. Specific outcomes are outlined in the measures section.

Methods and Measures

This is a community-engaged research collaboration between the non-profit Imprints Cares, the WFBMC Birth Center, and WFSOM. Because YMP is a tiered program model, services meet parents where they are through a “warm hand-off” approach that uses on one-on-one consultation and assessment-based interventions. The YMP is designed to address systemic barriers to the health and stability of young moms and their children such as the lack of coordination of service delivery or logistical barriers within the health system. The YMP also streamlines the referral pipeline, connecting

Protocol version:

Template updated 9.24.14

moms to evidence-based resources, and ensuring children complete all recommended assessments prior to kindergarten.

This research project is a pilot randomized controlled trial. We expect a total of 30 participants, 15 in each arm of the study. For inclusion into this study participants must be an immediately post-partum mother, between 14-21 years of age who will reside with her newborn. The mother must be referred from either the Birth Center at Wake Forest Baptist Health or from one of the Wake Forest Baptist Health PPC partner practices. Exclusion criteria include that newborn of participating mothers must be ≥ 35 weeks of gestation and not have an extended NICU stay. These populations are excluded because medically complex newborns and a prolonged separation during the intervention period will directly affect our outcome measures. Participants must speak English or Spanish given our parent educators and other group participants are limited to those languages. Males are excluded as participants, the intervention and many of the outcome measures are only applicable to female participants.

Participants will be randomly assigned to one of the two variants of the Parents as Teacher home visitation model, traditional or hybrid. The study's research coordinator, who is not directly involved with the delivery of services, will manage the randomization and assignment process; all consented participants will be given a system-generated unique identifier, which cannot be linked to patient identity by anyone except the research coordinator. This information will be securely maintained by the research coordinator. The team will complement the treatment groups' data with population data extracted from WFBMC's Epic system. Analysts will use rigorous techniques (e.g, Propensity Score Matching) to create a matched control group.

Both formats and all interventions included in the study are the current models of care for our existing PAT/YMP services. The hybrid model was developed in 2020 in response to the need to move services virtually as home visitation was not allowed during COVID-19 lockdown.

Through the traditional PAT model, participants will be referred through a warm hand-off from the Birth Center or one of WFBH community pediatric centers to Imprints Cares. A PAT certified family educator will meet with the family focusing on a one-on-one consultation and assessment-based interventions. Participants in the traditional PAT model will receive two home visits a month and participate in monthly peer (group) connections throughout the study period.

In the hybrid PAT model, participants will be referred through a warm hand-off to Imprints Cares from the Birth Center or one of WFBH community pediatric centers. A PAT certified family educator will meet with the family focusing on a one-on-one consultation and assessment-based interventions. Study participants will begin receiving services by participating in the virtual "What You Do Matters" program, an evidence-based PAT curriculum. After completion of the virtual program, young moms will begin receiving once a month home visits and participate in monthly peer (group) connections.

Protocol version:

Template updated 9.24.14

By including two variants in this pilot project, the study team will assess the cost-effectiveness of the two approaches, against short-term outcomes, which in turn will serve as leading indicators of longer-term results. At the end of the official study period, participants will be eligible to continue in the program until the child's school entry into kindergarten.

Both models will be staffed by qualified family educators that have been trained in the Parents as Teachers Foundational Curriculum, the Circle of Security model, and breastfeeding educator certification program. Imprints Cares also has a mental/behavioral health family educator on staff to address emergent mental/behavioral concerns as they arise. These approaches have been documented to nurture parental attachment and secure relationships^{xi}.

Outcome Measures

The team will use several published assessments:

Protective Factors Survey. The Protective Factors Survey (PFS) is a validated parent survey designed that assesses protective factors in five areas: family functioning/resiliency, social support, concrete support, nurturing and attachment, and knowledge of parenting/child development. The PFS will be implemented at week one, week six, and end of study, as it requires parent-child interactions for completion.

Ages and Stages Questionnaire 3rd edition. The Ages and Stages Questionnaire (ASQ 3) is a validated developmental screening designed for use by and with parents. The ASQ 3 screens for developmental milestones in communication, gross motor, fine motor, problem solving, and personal-social skills. The ASQ 3 will be implemented at the recommended intervals designed by its publisher (2, 4, and 6 months).

Ages and Stages Questionnaire: Social-Emotional 2nd edition. Similar to the ASQ 3, the Ages and Stages Questionnaire: Social-Emotional (ASQ:SE 2) is a validated screening of social and emotional behaviors. The ASQ:SE 2 will be implemented at the recommended intervals designed by its publisher (2, 4, and 6 months).

Patient Health Questionnaire. The Patient Health Questionnaire (PHQ 9) is a self-administered questionnaire that is validated for use in assessing the severity of depression. The PHQ 9 will be administered as a baseline assessment as well as an end-of-study assessment.

StimQ2-I. The StimQ2-I is a validated, interview-based assessment of home environments for use with infants ages five to 12 months. The StimQ2-I focuses on cognitive stimulation by the primary caregiver and contains several scales: Availability of Learning Materials, Reading-Verbal, Parental Involvement in Developmental Advance, and Parental Verbal Responsivity. The StimQ2-I will be implemented at the end of study, as it requires parent-child interactions for completion.

In addition to these assessments, the team will use an intake questionnaire to capture parent demographic and health information as well as baseline knowledge about child development and parenting and a monthly questionnaire used to assess mother's status on continuance of secondary education, breastfeeding, and use of contraception. A monthly questionnaire, which will be developed for use in this study, also will assess infant developmental milestones.

Further, the team will access health information captured in WFBMC's Epic system, including completion of Well-Child Visits and recommended immunizations. A WFBMC study team member will extract data on participants as well as a matched control group. The study team will conclude the study with participant focus groups, to collect additional qualitative feedback and insights. Finally, the team will develop and implement Fidelity of Implementation (FOI) quality

Protocol version:

Template updated 9.24.14

assurance guidelines and checklists to capture the degree to which project services are delivered as expected. FOI scores will be used as a predictive variable with the goal of establishing a minimum service threshold for short-term outcomes.

Proposed Statistical Analyses

Descriptive Analyses. All data will be subject to descriptive analyses, including measures of central tendencies and frequency distributions, as appropriate for the type of data collected. Descriptive analyses will support our understanding of participant characteristics and equivalency of samples in the traditional and hybrid models.

Inferential Analyses. Inferential analyses, such as t-tests, multiple regression, and Analysis of Variance, will be conducted to test for change between baseline and end-of-study data collections with the PHQ 9, and the PFS. The PFS will be administered at service week one, service week six, and at the end-of-study to assess differences between the models at promoting protective and nurturing behaviors. Tests also will be used to assess differences between the models on maternal outcomes such as continuance of secondary education, breastfeeding, and use of contraception and child-focused outcomes such as STIMQ2-I, completion of Well Child Visits and immunizations. The study team will work with CTSI Biostatistical Support services to advise and guide the analytic approach.

Proposed Cost Effectiveness Study Design. One of the primary challenges of completing cost studies is fully accounting for all costs and benefits. Therefore, the study team will use this project period to identify the spectrum of costs associated with serving one young mother and her child. These data will be compiled to generate an average cost of service and establish outliers that exist when there are particularly risky or traumatic cases. In addition, the team will establish short-term benefits (achievable after six-months of services) along with the program implementation conditions necessary to achieve them. We will utilize the services of BERD and Q-Pro to assist in advising in areas of study design, data analysis, and data management.

Study Timeline

Study Milestone	M1	M2	M3	M4	M5	M6	M7	M8	M9	M10	M11	M12
Achieve IRB approval	•											
Enrollment of teen moms		•	•	•								
Baseline data collected		•	•	•								
Services delivered	•	•	•	•	•	•	•	•	•	•		
Week one data collected	•	•	•									
Week six data collected		•	•	•								
ASQ/ASQ-SE data collected (2,4, and 6m)			•	•	•	•	•	•	•	•	•	•
Monthly questionnaires and FOI checklists completed			•	•	•	•	•	•	•	•	•	
End of study data collected											•	•
Analysis and reporting completed												•

The project will track numerous milestones, including:

- Submission of IRB application and receipt of IRB approval. This milestone is critical as the project will not move forward without IRB approval.
- Enrollment of young moms by the project's four month. All participants will need to be enrolled by month four to ensure moms in both models can receive at least six months of home visitation services. In the traditional model, home visitation starts immediately upon

Protocol version:

Template updated 9.24.14

enrollment. In the hybrid model, home visitation starts at the completion of the six-week What You Do Matters virtual class.

- Collection of all baseline data. Baseline data will be collected at the time of enrollment and will consist of the enrollment form and the PHQ 9.
- Collection of week one and week six data. Data will be collected during the participant's first and sixth week (at the close of the What You Do Matters course) of services in both models (PFS).
- Collection of monthly questionnaires. Monthly questionnaires will be implemented with each participant, on a schedule developed by the family educator.
- Collection of ASQ and ASQ:SE data as recommended by the publisher (2, 4, 6m).
- Collection of end-of-study data (6 months after enrollment). In the final month of services, the team will collect the ASQ, ASQ:SE, PHQ 9, the PFS and the StimQ2-I.
- Collection of FOI checklist data. Project staff and supervisors will complete FOI checklists on a monthly basis. Each model will have its own checklist.
- WFBMC data extraction and compilation of analysis files. One of the WFBMC team members will work to securely extract health data for treatment and matched control group participants from the Epic system.

Human Subjects Protection

Subject Recruitment Methods

No additional PHI will be accessed or printed/transcribed above and beyond what is part of standard patient care and pre-defined job descriptions.

OB Home Visiting Staff

- 1) Our OB Home Visiting Nursing Staff as part of their standard workflow identify and visit all post-partum mothers that reside in Forsyth County, NC.
- 2) Of those, they will identify mothers that meet inclusion criteria for the study (14-21 years old, Spanish or English Speaking, will reside with their newborn upon discharge, and will follow up with a Wake Forest Baptist Health Pediatrician).
- 3) During their standard meeting, while the mother is still inpatient from her delivery, OB home visiting staff per their standard workflow will ask if the mother would like referral to Imprints Cares. If they identify a likely eligible participant, they will introduce study at that time, without promising the patient they are eligible. If the patient is interested in referral for either the study or services not provided as part of the study, the team will make a referral to Imprints Cares. The referral will indicate if the patient appears to be eligible for the study or not.

Imprints Cares

- 1) After referral from the PPC primary care physician or the OB Home Visiting Nursing Staff to the Imprints Cares program, intake staff will assess if new mothers meet criteria for participation in the study (14-21 years old, Spanish or English Speaking, will reside with their newborn upon discharge, and will follow up with a Wake Forest Baptist Health Pediatrician).
- 2) Imprints Cares intake staff will ask if the mother would like to participate in the study, explain the risks and benefits, and obtain consent/assent from all required parties. This may be done in person if at the time of a clinic or intake home/community visit OR remotely via secure Docusign.
- 3) Imprints Cares staff will not directly benefit if a patient does or does not consent to the study, and patients are eligible for services if they do not consent, therefore it is not an undue influence to enroll patients.

Protocol version:

Template updated 9.24.14

Informed Consent

Signed informed consent/assent and parental permission to participate will be obtained from each subject as defined by participant age. Informed consent/assent and parently permission to participate will either be obtained in person if at the time of a clinic visit or intake home/community visit OR remotely via secure Docusign at by Imprints Cares Intake Staff approved as study staff by the IRB.

Confidentiality and Privacy

Confidentiality will be protected by collecting only information needed to assess study outcomes, minimizing to the fullest extent possible the collection of any information that could directly identify subjects, and maintaining all study information in a secure manner. To help ensure subject privacy and confidentiality, only a unique study identifier will appear on the data collection form. Any collected patient identifying information corresponding to the unique study identifier will be maintained on a linkage file, store separately from the data. The linkage file will be kept secure, with access limited to designated study personnel. Following data collection subject identifying information will be destroyed at the time the newborn is 6 years old, consistent with data validation and study design, producing an anonymous analytical data set. Data access will be limited to study staff. Data and records will be kept locked and secured, with any computer data password protected. No reference to any individual participant will appear in reports, presentations, or publications that may arise from the study.

Data and Safety Monitoring

The principal investigator will be responsible for the overall monitoring of the data and safety of study participants. The principal investigator will be assisted by other members of the study staff.

Reporting of Unanticipated Problems, Adverse Events or Deviations

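### Epic is the only named source for well-child visits and immunizations, and no described data item identifies a randomized infant who leaves WFBMC care, so care received elsewhere may be misread as non-completion

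*Combined protocol and SAP*

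**What the plan says.** Under Outcome Measures, the protocol says that the team will draw on health information in the medical center's "Epic system, including completion of Well-Child Visits and recommended immunizations". The milestone list under Study Timeline has a team member "securely extract health data for treatment and matched control group participants from the Epic system". No second source for visits or vaccines is named in either place.

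The Inferential Analyses paragraph includes these outcomes among the tests of differences between the models: "child-focused outcomes such as STIMQ2-I, completion of Well Child Visits and immunizations".

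Under Subject Recruitment Methods, both the OB home visiting staff and the Imprints Cares intake staff apply a criterion that the mother "will follow up with a Wake Forest Baptist Health Pediatrician". The inclusion text in Methods and Measures does not repeat it. Both checks come before follow-up begins.

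The other regular contact is "a monthly questionnaire used to assess mother's status on continuance of secondary education, breastfeeding, and use of contraception". On the infant's side, "A monthly questionnaire, which will be developed for use in this study, also will assess infant developmental milestones". Neither description mentions where the infant receives care. The documents give no coding rule for an infant who leaves the system, no plan to obtain outside records, and no missing-data method.

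**The concern.** The outcome is completion of care, so the absence of a record is itself informative. Epic can look the same for an infant who missed a visit and for one who was seen at a practice outside the system. A family that moves house or changes pediatrician during the six months can turn from the second case into an apparent instance of the first.

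The gap is in data capture as well as in analysis. Even an analyst who wants to set leavers to missing must know who left and when, and no described instrument collects that. With 15 infants per arm, a few misread records could noticeably change an arm's completion rate. These outcomes are also among the short-term results against which the cost-effectiveness of the two models is to be judged.

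**Working it through.** **Inputs from the documents.** 30 participants, 15 per arm (Methods and Measures); end of study six months after enrollment (Study Timeline). No completion rate, transfer rate, effect size or power is stated, so there is no figure of the plan's own to reproduce beyond 15 + 15 = 30. All rates below are assumptions.

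**Step 1: weight of one infant.** If completion is yes/no per infant, and a leaver who would have completed is read as not completing, the arm's proportion falls by 1/15 = 6.7 points. Two such infants give 2/15 = 13.3 points and three give 3/15 = 20 points. This is an upper limit per infant. If completion is scored as the share of due items done, a leaver loses only the items due after leaving. With a fraction f of items still to come, the shift is f/15, for example 0.5/15 = 3.3 points at f = 0.5.

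**Step 2: would there be any leavers?** Let m be the share of infants leaving over six months. Expected leavers per arm = 15m. Chance of at least one among 30 = 1 − (1 − m)^30.

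| Assumed m | Expected per arm | Chance of at least one in 30 |
|---|---|---|
| 5% | 0.75 | 78.5% |
| 10% | 1.5 | 95.8% |
| 20% | 3.0 | 99.9% |

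**Step 3: effect on the between-model comparison if blanks are read as non-completion.** If leaving is unrelated to completion, the observed rate = p(1 − m), where p is true completion.

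- Equal p and equal m in both arms: expected difference p(1 − m) − p(1 − m) = 0.
- True 90% vs 60% with equal m: the 30-point difference becomes 30 × (1 − m), that is 27, 24 and 21 points at m = 10%, 20% and 30%. Approximate power (15 per arm, two-sided 0.05) falls from 47% with no leavers to 35%, 26% and 20%. If leavers are excluded as missing instead, it is 43%, 39% and 35%.
- Unequal m, 5% vs 20%, with true 80% in both arms: 0.80 × 0.95 − 0.80 × 0.80 = 0.76 − 0.64 = 12 points of false difference. With true rates of 70% and 90% it is 10.5 and 13.5 points.

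**Step 4: chance imbalance under equal transfer.** Treating leavers in each arm as independent binomial(15, m), the chance that the arms differ by two or more leavers is 19% at m = 5% and 35% at m = 10%. For three or more it is 4% and 12%.

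**Step 5: would a false difference reach significance?** Two misread infants in one arm and none in the other, with all infants truly complete, gives 15/15 vs 13/15, Fisher p = 0.48. Three gives 15/15 vs 12/15, p = 0.22.

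**The case against.** A reader might infer that the plan scores an infant who leaves as not having received care. The documents do not support that. They say which record will be read, not how an absent entry is coded, and setting such an infant to missing is equally open.

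There are further points on the other side:

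- **Existing protection.** Two staff groups apply the pediatrician criterion, some families are referred by a partner practice and so already have contact with the system, and follow-up is only six months. This lowers the risk. It does not cover a change made after entry.
- **Informal knowledge.** Family educators see families twice a month in the traditional model, and monthly in the hybrid model once the six-week virtual class is over. They may well learn of a move, but no text asks them to record it.
- **Unseen forms.** The questionnaires sit with the IRB application, and the protocol lists their topics rather than their items. A site-of-care item could exist. The claim here is only that none is described.
- **Size.** The 6.7-point figure needs a yes/no outcome, which the plan does not specify, and a leaver who would otherwise have completed. No transfer rate or reason for imbalance is documented. The differing contact schedules make unequal leaving conceivable but do not show it. Steps 4 and 5 show that larger chance imbalances are the less likely case, and that two or three misread infants would not by themselves give a significant test.
- **Stakes.** This is a 30-participant pilot with many outcomes and none designated as primary.

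These points limit the size and certainty of the effect. They do not supply the missing information: a coding rule can be chosen at analysis, but departure dates that nobody collected cannot be fully recovered then.

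**Conclusion.** The point holds as a gap in ascertainment. A team following the plan exactly would have Epic alone for two outcomes compared between the models, and no described means of separating a missed visit from one made elsewhere. Misreading is possible, not prescribed.

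If it occurs, and completion is yes/no per infant, the effect is up to 6.7 points per misread infant in an arm of 15. Equal transfer attenuates a real difference by the factor (1 − m). Only unequal transfer or chance imbalance creates a false difference. Every transfer and completion rate used here is assumed.

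The change is worth making because it is cheap and the information is best captured during follow-up. It does not put the pilot as a whole in doubt.

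**What to change.** 1. Add one item to the monthly questionnaire, which is still to be developed: where the infant now receives well-child care and, if this has changed, the date.
2. For the randomized between-model comparison, count visits and vaccines due up to that date as done or missed according to Epic, and treat later ones as unobserved.
3. Report the number of leavers by arm, and show a sensitivity analysis in which the later items are coded as not completed.
4. For participants against matched controls, use the same Epic-only coding in both groups. No questionnaire is described for controls, so censoring participants alone would make ascertainment differ between the groups.

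The cost is one question and a short analysis rule. The item relies on mothers' report, and a mother who leaves the practice and also stops answering stays unidentified. Fewer due visits contribute for infants who leave. Leaving may itself be related to completion, so treating later items as unobserved is an assumption, and the sensitivity analysis shows how much depends on it.

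### With 15 mothers per arm and a separate fidelity checklist for each model, the pilot cannot support the minimum service threshold it sets out to establish

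*Combined protocol and SAP*

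**What the plan says.** The last paragraph of Outcome Measures says that the team will write FOI quality "assurance guidelines and checklists to capture the degree to which project services are delivered as expected". It then states the use: "FOI scores will be used as a predictive variable with the goal of establishing a minimum service threshold for short-term outcomes". The Study Timeline milestones add that "Project staff and supervisors will complete FOI checklists on a monthly basis" and that "Each model will have its own checklist".

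Methods and Measures gives the size and status of the study: "We expect a total of 30 participants, 15 in each arm of the study" and "This research project is a pilot randomized controlled trial". The planned service differs by arm. For the traditional arm, "Participants in the traditional PAT model will receive two home visits a month"; the hybrid arm has a virtual course first and then one home visit a month. Both have monthly groups.

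The documents do not state how a threshold would be chosen, for which outcome, at what significance level or with what validation. They do not say whether the arms are pooled, how the two checklists are put on one scale, or whether FOI is scored per mother, per educator or per model.

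**The concern.** A threshold is a stronger claim than an association: it names the level of service below which benefit is not expected. The plan gives no threshold in advance, so it would have to come from these data. Three features make that unsafe.

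- **Size.** A cut-off chosen from 15 or 30 observations is often a chance finding. Even when a real step exists, its position is poorly located.
- **Scale.** Scores from two different checklists are not on a common scale. If they are pooled without allowing for arm, the FOI score partly stands in for arm.
- **Non-randomised exposure.** Fidelity is observed after randomisation. If delivered service depends partly on how available the mother is, FOI carries her engagement with it.

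At stake is a pilot finding being carried forward as a minimum dose of service when the data could not identify one.

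**Working it through.** **Inputs.** From the documents: 30 mothers, 15 per arm, and one checklist per model. Assumed, because not stated: two-sided 0.05, normal outcomes, FOI scored per mother, no dropout, and the effect sizes, offsets and correlations named below. The plan gives no power or precision figure for the threshold, and the sample of 30 comes without inputs, so there is no figure to reproduce.

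**1. Scanning for a cut-off with no true relation.** With at least m mothers on each side there are n − 2m + 1 possible cuts. For m = 3 this is 15 − 6 + 1 = 10 within one arm and 30 − 6 + 1 = 25 pooled. The largest |t| over these cuts is compared with the ordinary two-sided 5% t limit on n − 2 degrees of freedom. Simulation (3,000 to 40,000 replicates) gives:

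| | n=15 | n=30 |
|---|---|---|
| m = 3 | 23-24% | 35-36% |
| m from 5 down to 2 | 15-29% | 29-39% |

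**2. Several outcomes.** Eight measures are named in Proposed Statistical Analyses: PHQ 9, PFS, education, breastfeeding, contraception, StimQ2-I, well-child visits and immunizations. How many would be tried against FOI is not stated. For five independent outcomes and m = 3:

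- n=15: 1 − (1 − 0.241)^5 ≈ 75%
- n=30: 1 − (1 − 0.353)^5 ≈ 89%

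With outcomes correlated at 0.5 the figures are 66% and 81%. Without any scan, one fixed cut per outcome gives 1 − 0.95^5 = 23% for five independent outcomes and 1 − 0.95^8 = 34% for eight.

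**3. Locating a real threshold.** With a true step of 0.8 SD at the median, the estimated cut lies within 10 percentile points of the truth in 45% of trials at n=15 and 57% at n=30. The central 95% of estimated cuts runs from the 20th to the 80th percentile (n=15) and from the 10th to the 90th (n=30).

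**4. One pre-specified median split.** At 80% power the smallest detectable difference (exact t) is 1.06 SD for 15 v 15 pooled and 1.57 SD for 7 v 8 within an arm. By the normal approximation, n per group = 2(1.96 + 0.84)²/d²: 63 for d = 0.5 and 25 for d = 0.8.

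**5. Pooling two checklists, no fidelity effect.** A linear regression on FOI with 15 per arm gives these false-positive rates:

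| Arm effect on outcome | Checklist offset | No arm term | With arm term |
|---|---|---|---|
| 0 | 2 SD | 5% | 5% |
| 0.8 SD | 0 | 5% | 4% |
| 0.8 SD | 1 SD | 14% | 5% |
| 0.5 SD | 2 SD | 15% | 5% |
| 0.8 SD | 2 SD | 30-31% | 5% |

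The inflation needs both an offset and an arm effect, and the arm term removes it.

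**6. Precision of a slope within one arm.** For an observed r = 0.5 at n = 15, Fisher's z = atanh(0.5) = 0.549 with standard error 1/√12 = 0.289. The interval 0.549 ± 1.96 × 0.289 is −0.016 to 1.115, which back-transforms to −0.02 to 0.81.

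**7. Engagement, as a what-if.** If engagement correlates 0.5 with both FOI and outcome, the induced correlation is 0.5 × 0.5 = 0.25, and a pooled scan finds a cut in 61% of trials with no fidelity effect. With both correlations 0.3 (induced 0.09) the figure is 39%. The baseline from step 1 is 35-36%.

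**The case against.** The strongest reply is that the plan names no scan and no pooling. FOI is called a predictive variable, and the listed methods include multiple regression, so a continuous FOI term fits the text. Separate checklists are as consistent with within-model analyses as with pooling. The study is a self-described pilot, FOI is a small ancillary item, and biostatistical advisers are to guide the analysis.

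Much of this stands, and it rules out several stronger readings that a reader might infer:

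- **That the plan will produce a chance cut-off.** Even under a scan, most null trials yield none for a single outcome.
- **That FOI is confounded with arm.** This requires pooling without an arm term, plus arm differences in both score and outcome. Within-arm analysis avoids it, but leaves n=15. If FOI were scored per model, it would be wholly aliased with arm; the scoring unit is not stated, and the n=15 and n=30 calculations assume the mother.
- **That FOI is confounded with maternal engagement.** FOI is defined as service delivery and the checklists are unwritten. This is a reasonable possibility, not a documented fact.
- **That the threshold feeds the cost-effectiveness work.** Proposed Cost Effectiveness Study Design speaks of short-term benefits "along with the program implementation conditions necessary to achieve them", but does not tie these conditions to FOI scores.
- **That the comparison of the two models depends on FOI.** No section conditions it on fidelity.

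What the reply does not answer is the stated goal. A continuous regression gives a slope, not a minimum, so reaching a threshold still requires choosing a cut. Pilot status is a reason not to claim one, and a promise of advice does not specify a method.

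**Conclusion.** The concern holds in a conditional form. The goal of establishing a minimum service threshold is beyond what 15 mothers per arm and two non-equivalent checklists can support, by either route. A within-arm analysis has n=15, where a scan gives a chance cut in about 23% of null trials and a fixed median split detects only about 1.57 SD. A pooled analysis has n=30, where a scan gives 35-36%, and leaving out the arm term can give false associations in about 15-31% under the assumed 2 SD offset and 0.5-0.8 SD arm effect. Because FOI is not randomised and may partly reflect engagement, an observed relation cannot be read as the effect of service.

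The percentages rest on the assumptions listed with the working, and the plan does not commit to either analysis. The conclusion that no threshold should be claimed does not depend on which one is chosen.

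**What to change.** Replace the threshold goal in Outcome Measures with an exploratory analysis that selects no cut-off and claims no minimum from this pilot. Specify that:

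- FOI is scored per mother, and the outcome or outcomes it is related to are named in advance.
- FOI stays continuous and is standardised within arm.
- The result is the two within-arm slopes, or one slope from a model containing the arm term, with 95% CI. The single slope assumes that 1 SD means the same on both checklists; the within-arm slopes do not.
- The result is labelled hypothesis-generating and described as an association.

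A shared item on both checklists, the percentage of that model's planned contacts delivered, is optional. It would give a common scale, but it depends on attendance and does not remove confounding by engagement.

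The cost is one reworded aim and a few lines of specification; the checklists are still to be developed, and no participants or visits are added. The downside is that the pilot cannot announce a service threshold. This is a cheap improvement.
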